### **5.3.6 Control Group**

Each participant’s health history will be collected before the blood draw to determine the health and safety of each participant during the venipuncture procedure. The participant’s self-reported medical history is reviewed by trained study staff to assess any medical history that would place a participant at increased risk during a blood collection.

If the participant qualifies for the control group and a researcher has requested the maximum blood volume to be collected, the study staff must assess the health of the participant to determine if they are healthy enough to undergo a 180mL blood draw. The following questions are asked to the participant to assess the safety during the 180mL blood draw:

*Must answer “YES” to all questions in order to be considered for 180mL draw*

1. Is the participant's weight  $\geq 110$ lbs?
2. Is the participant younger than 85 years old?
3. Does the participant have difficulties with blood draws (e.g., hard stick)?

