Drawing up to 100mL for the health condition group will allow the biobank to collect enough blood from isolating several sub-products from the whole blood, such as serum, plasma, peripheral blood mononuclear cells (PBMCs), and genetic material (DNA/RNA), which are commonly used in biomedical research. A blood draw will provide biological tissue to research and expose participants to minimal risk. A blood draw allows participants flexibility in scheduling the draw, either at a site or in the comfort of their home.

Due to a potential increase of phlebotomy risks for people with certain medical conditions such as cardiovascular diseases, bleeding disorders and late-stage kidney problems, the exceptive condition group will have only up to 60mL drawn to minimize these risks.

The study aims to collect biological tissue from multiple populations to support and advance biomedical research. Drawing a large volume of blood from healthy donors will provide more control biosamples for researchers (posing minimal risk to the participant). Allowing the study efforts to concentrate on collecting samples from various populations to service more research fields.

The control group may have up to 180mL of blood drawn for the study if determined that the participants health will not compromise their safety during the draw. The amount of 180mL is about one-third of the blood drawn during a blood donation and is considered by the Department of Health and Human Safety (HHS) to pose minimal risk to the participant. The study would like to have the potential to draw up to 180mL if the health of the participant allows this amount biological tissue to be collected from one appointment. Since the major risk and discomfort from venipuncture comes from being stuck with the needle, the study believes that a one-time blood draw of a larger volume would be potentially more comfortable for a healthy individual versus undergoing multiple venipunctures.

Participant health will be assessed prior to phlebotomy to determine maximum blood draw volume for all cohorts.

For all research requests that are not covered within this protocol, independent protocol amendments addressing the procedural changes may be drafted to address and minimize possible study risks. A medical practitioner will review the procedural amendments for safety assessment and submit to the IRB for review.

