##### **5.3.5.1 Blood Collection**

A blood draw is the most common type of biospecimen collection procedure, making up about

95% of biospecimen requests. Blood will generally be collected by venipuncture from a medical professional certified in phlebotomy. Participants may also be asked to provide a microsample of blood via fingerstick. Fingerstick samples will be collected on a blood card, such as a dried blood spot (DBS) card, or into a microtainer. Researchers may use the blood cards for specific testing of biomarkers or isolating genetic material.

Blood collection volumes are dependent on which cohort the participant is placed and self-reported medical data (see Table 1). Blood may be collected every 7 days, but the total volume collected during a 6-week period may not exceed the Table 1 volumes. Maximum blood collection volumes in Table 1 may be collected at one time

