**Table 1: Maximum Blood Collection Volume by Cohort**

Cohort	Blood Draw Volume (mL)
Health Condition	≤100mL
Exceptional Condition	≤60mL
Control	≤180mL

The maximum blood collection volume within a 6-week period by cohort.

Participants within the health condition and control groups who weigh less than 110 pounds and/or are older than 85 years old will have a maximum collection volume of 75mL within a 6-week period.

Before the phlebotomy procedure, a Sanguine designated phlebotomist will assess the participants health by asking questions like, “Do you feel healthy today?” and noting any physical symptoms that may require the blood draw to be aborted. The phlebotomist then decides if the blood draw can continue as scheduled. The blood draw appointment follows phlebotomy best practices set forth by the College of American Pathology (CAP) and the World Health Organization (WHO). Venipuncture is attempted no more than 3 times. After a third failed attempt, the blood draw is canceled. After the blood draw, the phlebotomist will remain with the participant until the wound has successfully clotted and/or the participant reports that they feel well enough to resume light activities.

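### The 180 mL control checklist demands YES to every question, but on question 3 YES means the participant is hard to draw from

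*Protocol*

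**What the plan says.** Section 5.3.6 of the Protocol applies when a participant qualifies for the control group and a researcher has asked for the maximum volume. Staff must then judge whether the participant is fit for a 180 mL draw. The purpose of the checklist is given as: "The following questions are asked to the participant to assess the safety during the 180mL blood draw". The scoring rule is: "Must answer “YES” to all questions in order to be considered for 180mL draw".

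The three questions ask:

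1. whether weight is at least 110 lbs;
2. whether the participant is younger than 85;
3. "Does the participant have difficulties with blood draws (e.g., hard stick".

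Other sections also bear on draw volume.

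- Section 4.1 gives the reason for the larger control volume: "Drawing a large volume of blood from healthy donors will provide more control biosamples for researchers". It allows 180 mL only where the participant's health does not compromise safety, and adds a general check: "Participant health will be assessed prior to phlebotomy to determine maximum blood draw volume for all cohorts".
- Section 5.3.5.1 states: "Blood collection volumes are dependent on which cohort the participant is placed and self-reported medical data".
- The text under Table 1 caps health condition and control participants who weigh under 110 lbs or are older than 85 at 75 mL in six weeks. It also provides a pre-draw check by the phlebotomist and a limit on attempts: "Venipuncture is attempted no more than 3 times".
- Section 5.2 puts eligibility and medical history under a medical doctor's oversight.

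**The concern.** The checklist mixes two directions of wording under one scoring rule. YES is reassuring on weight and age. YES on question 3 reports a problem. An all-YES rule therefore turns the third item from a bar into a requirement.

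This is a mandatory decision rule, and the only checklist in the visible text that is specific to the largest volume in Table 1. Staff who apply it as written let hard-stick controls through to consideration and turn away easy-draw controls as donors for the single 180 mL draw. Staff who apply what was evidently meant depart from the protocol each time. A screening form copied from section 5.3.6 would carry the reversal with it.

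No endpoint, sample size or analysis depends on this. What is at stake is a safety gate that cannot be followed as written and still do its job.

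**Working it through.** There is no stated figure to reproduce. The check is a truth table over the possible answers.

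**Inputs (all from Protocol section 5.3.6 unless noted)**

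- Rule: YES to questions 1, 2 and 3.
- Favourable answer to question 1: YES. Table 1's note supports this direction, since it caps those under 110 lbs at 75 mL.
- Favourable answer to question 2: YES. The same note caps those older than 85.
- Favourable answer to question 3: NO, because YES reports difficulty.
- Purpose: safety during the 180 mL draw.

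**All answer patterns.** Three yes/no items give 2 × 2 × 2 = 8 patterns.

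| Q1 weight | Q2 age | Q3 difficulty | Rule as written | Rule that fits the purpose |
|---|---|---|---|---|
| YES | YES | YES | considered | not considered |
| YES | YES | NO | not considered | considered |
| the other 6 patterns, with NO to Q1 or Q2 | | | not considered | not considered |

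As written, 1 of 8 patterns passes, and it belongs to a participant with draw difficulty. The pattern that fits the purpose (heavy enough, young enough, easy to draw from) fails.

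**Controls who meet the weight and age items.** Two patterns remain. The written rule passes one and the purpose-consistent rule passes the other, so the overlap is 0. This follows from reversing one binary item and needs no rate.

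**Illustration per 100 such controls screened for the maximum volume.** Let d be the share with draw difficulty. The protocol gives no value, so 5% to 30% is assumed. The written rule considers 100d and bars 100(1 − d).

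| d (assumed) | Considered, all with difficulty | Barred, all without difficulty |
|---|---|---|
| 5% | 5 | 95 |
| 10% | 10 | 90 |
| 20% | 20 | 80 |
| 30% | 30 | 70 |

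These figures only restate d and 1 − d. They show who would be sorted which way, and do not measure impact.

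**Does another section correct question 3?**

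- Section 4.1 (health assessed before phlebotomy): general, with no mention of draw difficulty.
- Section 5.2 (physician oversight): general.
- Section 5.2.3 (control exclusions): lists medical conditions, pregnancy, recent donation and the like, but not draw difficulty.
- Section 5.3.5.1 (volume by cohort and self-reported data): names no such item.
- Text under Table 1 (phlebotomist's check, three attempts): limits failed sticks at the visit, but sets no volume condition.
- Section 5.3.6 (history review): looks for medical history that raises risk and leaves the scoring of question 3 as it is.
- Appendix C (health profile): the visible part records weight and has no draw-difficulty field.

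None of these reverses the item. The content of the participant safety flow in Appendix B is not visible, so this result covers the visible text only.

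**After the change.** If question 3 is worded so that YES means free of difficulty, the all-YES rule again passes exactly one pattern: at least 110 lbs, younger than 85, no draw difficulty.

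**The case against.** The best case on the other side accepts the wording error and disputes its weight.

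- **The intent is plain.** The sentence introducing the checklist and the first two questions tell any reader what was meant. This stands. It makes a literal application unlikely, but does not make the text correct.
- **Other safeguards remain.** YES only permits consideration, the checklist is used only on maximum-volume requests, a doctor oversees eligibility, and the phlebotomist can stop the draw. All of this stands and limits the practical reach.
- **Easy-draw controls are not lost altogether.** Section 5.3.5.1 allows blood every 7 days up to the six-week maximum, so a control barred from the single draw could give less at one visit, and apparently reach the same 180 mL over several. This stands: the loss concerns only the one-time draw. Section 4.1 does prefer one large draw to repeated venipuncture for a healthy individual, so some cost remains.
- **The conflict with section 4.1 is thin.** That section speaks of healthy donors, and a person with difficult veins may be healthy. This is fair. The real contradiction lies within section 5.3.6, between question 3 and the checklist's own purpose. Section 4.1 is background.
- **The per-100 figures carry no evidence.** Agreed: they rest on an assumed rate, and the truth table is enough without them.
- **The working form or Appendix B may word the item correctly.** That is possible and cannot be checked here. If so, section 5.3.6 would conflict with it and would still need correcting.

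**Conclusion.** The concern holds. Section 5.3.6 is wrong as written: followed literally, it sorts every control who meets the weight and age items the wrong way on question 3. That conclusion assumes only that the item was meant to screen out draw difficulty, which is the one reading that fits the stated safety purpose.

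The number of participants affected cannot be computed. The protocol gives no rate of draw difficulty, section 5.1 leaves the control total undetermined, and staff may follow the intent. The protocol does not link draw difficulty to poor tolerance of volume, so no specific harm is asserted. Confidence is high on the wording and cannot extend to what happens in operation. Because this is an operative rule on the largest draw volume, it should be fixed, though it does not undermine the study.

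**What to change.** Either change is sufficient:

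- reword question 3 to *Is the participant free of difficulties with blood draws (for example, not a hard stick)?* and keep the all-YES rule; or
- keep question 3 and change the rule to *YES to questions 1 and 2 and NO to question 3*.

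The first is safer on a form, because every item then points the same way. Whichever is chosen, check the Appendix B safety flow and any screening form that uses these questions, and align them. The cost is one line of protocol text plus any such form. No procedures or participants are added.

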### **5.3.7 Optional Biospecimen Collection**

Participants may be asked to donate other biospecimens such as saliva, stool, urine, sputum, semen, hair, nail clippings, skin cells from a skin or swab or skin taping strips, cells from the mouth via buccal swab, and respiratory mucosa or nasal samples from a nasal or nasopharyngeal swab. The collection methods of these biospecimens are considered no more than minimal risk to the participant.

Participant facing visit guides may be created for any required self-collections. This documentation will be approved by the IRB for approval prior to any applicable collection taking place.

### **5.3.8 Participant surveys, questionnaires, and PROs**

Participants may be asked to complete a survey, questionnaire, or PRO, either in conjunction with a biospecimen collection or following a separate, variable schedule.

Sanguine sends a single question, non-study specific survey to participants post-screen, and post-scheduled appointment for feedback on their experience.

### **5.3.9 Recovery Time**

Depending on how much blood is drawn, pertinent health history (including current medications), and other tissue donation procedures performed, the phlebotomist and/or study staff will determine how much time a participant will need to recover from the procedure. Steps to recovery include hydration, a snack, and a period of rest before performing strenuous activities or heavy lifting. Phlebotomists will remain with the participant after the phlebotomy procedure to ensure proper clotting and the participant feels well-enough to perform daily activities.

After the visit is completed, Sanguine will send a post-visit survey to the participants for feedback on their experience. Refer to Appendix D for a survey example.

### **5.3.10 Collection of Protected Health Information (PHI)**

Participants will have their protected health information collected in two ways: self-reported data and a thorough review of their medical records. Upon enrollment, participants will be asked to authorize the release of their health information. Participants who deny this authorization may affect their enrollment within the biobank study. Upon receiving this authorization, study staff will request medical data from the appointed healthcare provider. This data will be secured by physical, electronic, and administrative means.

The biobank has security measures to protect the participant's PHI and are discussed in Section 6 and Section 7.

## **5.4 Confidentiality/De-identification Process**

The research on the biospecimens will be performed without the use of the participant's names, pictures, address, or any government-issued identification numbers (such as social security number) or any other direct identifiers as stated in the Health Insurance Portability and Accountability Act (HIPAA). Participants will be randomly assigned a unique participant identifier. This number will be used to identify the participant on all documents.

### **5.5 Direct Access to Source Data/Documents**

The investigator and/or institutions involved in this study will agree to allow trained employees from Sanguine direct access to all source data and documents, including the participants complete medical records. Access must also be granted to authorized auditors, IRB reviewers, and all applicable regulatory bodies, as necessary.

### **5.6 Sample Processing and Storage**

Sanguine follows the International Society for Biological and Environmental Repositories (ISBER) and NCI repository best practices to assure quality biospecimen processing and storage. Guidelines for these best practices have been adapted to Sanguine's specific laboratory space and personnel and are specified in applicable lab procedures. In accordance with these guidelines and to assure quality, each type of biospecimen extracted and processed on behalf of the Sponsor follows a specific standard operating procedure.

Biospecimens extracted and processed by Sanguine for storage and redistribution to researchers include, but are not limited to, serum, plasma, PMBC's, DNA, and RNA. Biospecimens are stored in cryogenic containers. To control biospecimen quality the cryogenic containers are constantly monitored for temperature oscillations, which are recorded electronically. In the future, the biobank may store dehydrated samples at ambient temperature as approved and accepted by biorepository storage practices. As a part of the biorepository protocol, specimens will remain at Sanguine indefinitely or until they are distributed to an approved research study.

Detailed sample collection and shipping documentation will be provided to each site by Sanguine. Samples collected may be shipped overnight directly to the requesting researcher and/or designated third party, dropped off same-day to the requesting researcher, or shipped overnight to one of Sanguine's processing labs. Shipments may be frozen, ambient, or refrigerated. The lab verifies incoming samples before processing begins. All direct participant identifiers are blinded to the laboratory staff and researchers. Parent samples will be labeled with the unique participant identifier, as specified in the applicable lab procedures.

All procedures for collecting, handling, storing, and shipping biobank materials are specified in the biorepository standard operating procedures or specific study documentation. Sanguine follows the International Society for Biological and Environmental Repositories (ISBER) and NCI repository best practices to assure quality biospecimen processing and storage.

### **5.7 Biospecimen & Data Distribution Procedures**

Sanguine will provide quality biospecimens to institutionally approved pre-clinical and clinical investigator-led studies for diagnostic, therapeutic, and preventative research. Once the Sponsor receives an order for biospecimens and associated clinical records from a client, the Sponsor will

ship the requested biospecimens at either room temperature, refrigerated, or cryogenically to the client. The Sponsor will deliver the associated, redacted health information to the client either electronically or physically. Third parties receiving annotated biospecimens or access to the electronic biospecimen library must agree to Sanguine's terms and conditions and/or complete a Materials Transfer Agreement to minimize risks associated with the transfer of biospecimens and health information. Third parties must agree to use biospecimens for research purposes as specified in the informed consent and agree not to seek out the identity of participants.

The Sponsor will also provide potential client investigators with access to available de-identified biospecimens and clinical information (de-identified DNA sequences and associated de-identified electronic medical records and participants' self-reported but de-identified information) through a data tracking application.

## 5.8 Study Termination

Participants will be considered inactively involved in SAN-BB-02 indefinitely or for as long as their biospecimens and data remain stored within the biobank. A participants participation may be terminated partially or completely.

Guidelines for these best practices have been adapted to Sanguine's laboratory partners and personnel and are specified in Sanguine's SOPs.

## 5.9 Participant-Initiated Withdrawal

Participants have the right to withdraw from the study at any time. There is no penalty if the participant decides to end his/her participation. For a participant to withdraw from the study, a written or verbal request must be made to Sanguine's study staff. Participants do not need to give a reason for changing their minds. Biospecimens and health data may be handled after withdrawal in two ways:

1. **No Longer Interested.** The study no longer has contact with the participant, and the authorization for the release of information expires. The biobank still has permission to use all biospecimens and data stored within the biobank at the time of withdrawal.
2. **No Longer Interested - Destroy Remaining Samples/Data.** The study no longer has contact with the participant, and the authorization for the release of information expires. All samples and data remaining in the biobank are destroyed.

If it is not clear how the participant wants the samples and information handled from your written request, the Sponsor will treat the withdrawal as "No Longer Interested."

The biobank cannot recall samples and data that have already been given to third-party researchers.

## 5.10 Investigator-Initiated Withdrawal

The site investigator or Sponsor may remove a participant from the study at any time and for any reason. Since the biobank does not provide medical treatment or health care, there will be no penalty imposed upon the participant. Reasons for which the PI or site investigator may terminate a participant's enrollment may include but are not limited to: the participant does not follow study directions, or the Sponsor stops the study for any reason.

## 6 RISK/BENEFIT ASSESSMENT

### 6.1 Potential Risks

Potential risks associated with this study include physical and data-related risks.

Physical risks are those associated with venipuncture. At the time of the blood draw, the participant may experience a small amount of pain associated with introducing the needle into the skin, bruising at the venipuncture site, and a small risk of light-headedness or feeling faint, which are commonly associated with blood draws in general. There may also be slight discomfort or skin irritation due to hair sampling or skin taping.

This biorepository study is a study where biospecimens and associated medical data are stored indefinitely. Therefore, the main data-related risk is a breach of privacy. Though rare and unforeseen, a participant's private health information or identifiable information may become available outside the study. If a participant's insurance provider or employer becomes aware of the participant's study enrollment or experimental results associated with their specimens, the insurance provider or employer may participant the participant to health discrimination.

